5.3 Lifestyle Considerations

5.3.1 Meals and Dietary Restrictions

Abstain from consumption of the following from 14 days before the start of study intervention until after the final dose: Seville oranges, grapefruit or grapefruit juice, pomelos, exotic citrus fruits, grapefruit hybrids, cranberries, fruit juices or St John's Wort.

Products containing poppy seeds (cake, rolls) may not be consumed within 48 hours before Screening and each admission until discharge.

On Day 1 and Day 12, participants will receive a single dose of 500 mg tepotinib HCl hydrate (tablets) in the morning at the start of a standard moderate-fat/moderate-calorie breakfast. Following an overnight fast of at least 10 hours, participants should receive a standard moderate-fat/moderate-calorie breakfast which should be consumed within 30 to 60 minutes. The start date and time and stop time of the breakfast will be recorded in the participant's eCRFs as well as whether the entire breakfast was consumed. If the entire meal is not consumed, the percentage of meal consumed (in quartiles) should be recorded.

On Days 8 to 11 and Days 13 to 18, participants will receive once-daily a single dose of 200 mg itraconazole (capsules) taken immediately after the standard moderate-fat/moderate-calorie breakfast. On Day 12, participants will receive a single dose of 200 mg itraconazole (capsules) simultaneously with a single dose of 500 mg tepotinib HCl hydrate (tablets) in the morning at the start of a standard moderate-fat/moderate-calorie breakfast.

Study interventions will be administered with 240 mL of water in a standing position during the on-site stay at the CRU. On dosing days (see Schedule of Assessments in Section 1.3), participants may consume water ad libitum and should drink at least 1.5 L/day.

Standard moderate-fat, moderate-calorie breakfasts are defined as follows: 490 calories composed of approximately 77 g of carbohydrates, 28 g of protein, and 13 g of fat (Naderer 2015).

All other meals during the inpatient stay at the CRU will be standardized and no documentation of time and complete consumption is needed. The participants are only permitted to eat meals provided by the CRU. These meals will be provided at usual meal times of the CRU.

5.3.2 Caffeine, Alcohol, Tobacco, and Cannabinoid

- During each dosing period, participants will abstain from ingesting caffeine- or xanthine-containing products (e.g., coffee, tea, cola drinks, and chocolate) for 48 hours before the start of dosing until after collection of the final PK and/or PD sample.
- During each dosing period, participants will abstain from alcohol and cannabinoid-containing products for 48 hours before the start of dosing until after collection of the final PK and/or PD sample.
- Use of tobacco products will not be allowed from 6 months before the time of the Screening visit until after the final follow-up visit.

5.3.3 Activity

Participants will abstain from strenuous exercise for 72 hours before each blood collection for clinical laboratory tests. Participants may participate in light recreational activities (e.g., watching television or reading).

5.4 Screen Failures

Individuals who do not meet the criteria for participation in this study (screen failure) will not be rescreened.

5.5 Criteria for Temporarily Delaying the Administration of Study Intervention

Not applicable.

6 Study Intervention(s) and Concomitant Therapies

Study intervention is any investigational intervention(s), marketed product(s), placebo, or medical device(s) intended to be administered to a study participant per the study protocol.

6.1 Study Intervention(s) Administration

Intervention Name	Tepotinib (HCl hydrate)	Itraconazole
Type	Drug	Drug
Dose Formulation	Film-coated tablet	Hard-gelatin capsule
Unit Dose Strength(s)	250 mg	100 mg
Dose Amount	500 mg (2 tablets) with food	200 mg (2 capsules) with food
Frequency	Day 1 and 12 in the morning	Once daily at the same time in the morning (every 24 hours \pm 1 hour) from Day 8 to Day 18; on Day 12 itraconazole is administered concomitantly with tepotinib (Section 5.3.1).
Route of Administration	Oral	Oral
Use	Experimental	Experimental
Investigational Medicinal Product (IMP) and Non-Investigational Medicinal Product (NIMP)	IMP: tepotinib	IMP: itraconazole
Sourcing	Sponsor (Merck Healthcare KGaA)	Sponsor (Merck Healthcare KGaA)
Packaging and Labeling	Study intervention will be provided as blisters in screw-cap bottles that are packaged and labeled per all applicable regulatory requirements and Good Manufacturing Practice Guidelines. Details on packaging design and administration of tepotinib will be defined in the IMP Handling Manual.	Study intervention will be sourced as commercial packs and labeled per all applicable regulatory requirements and Good Manufacturing Practice Guidelines. Details on packaging design and administration of itraconazole will be defined in the IMP Handling Manual.

IMP=investigational medicinal product.

6.2 Study Intervention(s) Preparation, Handling, ~~CCI~~ and Accountability

The Investigator, institution, or the head of the medical institution (where applicable) is responsible for study intervention accountability, reconciliation, and record maintenance (i.e., receipt, reconciliation, and final disposition records).

- Upon receipt of the study intervention(s), the Investigator or designee will confirm appropriate temperature conditions have been maintained during transit and any discrepancies are reported and resolved before use. Also, the responsible person will check for accurate delivery. Further guidance and information for study intervention accountability are provided in the IMP handling manual.
- Only participants enrolled in the study may receive study intervention(s) and only authorized site staff may supply it. All study intervention(s) will be stored in a secure, environmentally controlled, and monitored (manual or automated) area, per the labeled storage conditions, and with access limited to the Investigator and authorized site staff.
- Dispensing will be recorded on the appropriate accountability forms so that accurate records will be available for verification at each monitoring visit.

- Study intervention(s) accountability records at the study site will include the following:
 - Confirmation of receipt, in good condition and in the defined temperature range.
 - The inventory provided for the clinical study and prepared at the site.
 - The dose(s) each participant used during the study.
 - The disposition (including return, if applicable) of any unused study intervention(s).
 - Dates, quantities, batch numbers, container numbers, expiry dates, and the participant numbers.
- The Investigator site will maintain records, which adequately documents that participants were provided the doses specified in this protocol, and all study intervention(s) provided were fully reconciled.
- Unused study intervention(s) will not be discarded or used for any purpose other than the present study. No study intervention that is dispensed to a participant may be redispatched to a different participant.
- A Study Monitor will periodically collect the study intervention(s) accountability forms.
- Further guidance and information for the final disposition of unused study intervention(s) are provided in the IMP handling manual.

6.3 Measures to Minimize Bias: Study Intervention Assignment and Blinding

6.3.1 Study Intervention Assignment

Not applicable as this is a nonrandomized study.

After informed consent procedure, every participant is given a screening number. Only participants who comply with all selection criteria (see Sections 5.1 and 5.2) can be included into the study. Prior to the first administration, the participants enrolled will be assigned to a unique 3-digits assignment number in ascending numerical order.

The Investigator will keep a record relating the participant assignment numbers and the names of all participants (including screening number and the Nuvisan GmbH identification number) who have given their informed consent, to allow easy checking of data in participant files, when required. This record will also include the date of participant's enrollment and completion, as well as participants who could not be assigned to study intervention for whatever reason.

6.3.2 Blinding

Not applicable. This is an open-label study.

6.3.3 Emergency Unblinding

Not applicable. This is an open-label study.

6.4 Study Intervention Compliance

When participants are dosed at the site, they will receive study intervention directly from the Investigator or designee, under medical supervision. The date and time of each dose administered in the clinic will be recorded in the source documents and recorded in the CRF. The dose of study intervention and study participant identification will be confirmed at the time of dosing by a member of the study site staff other than the person administering the study intervention. Study site personnel will examine each participant's mouth to ensure that the study intervention was ingested.

6.5 Dose Modification

Doses will not be modified.

6.6 Continued Access to Study Intervention after the End of the Study

The Sponsor will not provide any additional care to participants after they leave the study because such care would not differ from what is normally expected for healthy participants.

6.7 Treatment of Overdose

For this study, any dose of study intervention greater than the maximum dose in the study that is considered safe and well-tolerated within a 24-hour time period will be considered an overdose.

The Sponsor has no specific recommendation for treating an overdose of tepotinib. The Investigator will use his clinical judgment to manage any overdose, considering the symptoms and any site procedures or standards.

Recommendation for treatment of an overdose of itraconazole is described in the respective SmPC.

Even if not associated with an AE or a SAE, any overdose is recorded in the CRF and reported to global patient safety in an expedited manner. Overdoses are reported on a SAE and Overdose Report Form, following the procedure in [Appendix 4](#).

6.8 Concomitant Therapy

Record in the CRF all concomitant therapies (e.g., medicines or nondrug interventions) used from the time the participant signs the informed consent until completion of the study, including any changes. For prescription and over-the-counter medicines, vaccines, vitamins, and herbal supplements, record the name, reason for use, dates administered, and dosing information.

Contact the Medical Monitor for any questions on concomitant or prior therapy.

6.8.1 Rescue Medicine

No specific antidote is available for tepotinib. Symptomatic treatment will be provided in case of a medical emergency.

In case of toxicity during itraconazole treatment refer to the itraconazole SmPC and USPI.

6.8.2 Permitted Medicines

The only permitted medications are the following:

- Paracetamol/acetaminophen up to 2 g per day, at the discretion of the Investigator.

Any medicines that are considered necessary to protect the participant's welfare in emergencies may be given at the Investigator's discretion, regardless if it results in a protocol deviation.

Medications may be given at the Investigator's discretion if deemed necessary for the participant's immediate wellbeing. Medications may be administered to address adverse reactions or anticipated emergency situations.

The Investigator will record all concomitant medications taken by the participants during the study, from the date of signature of informed consent, in the participant source data and in the appropriate section of the eCRF.

6.8.3 Prohibited Medicines

Prohibited medicines at study entry are indicated in the exclusion criteria (Section [5.2](#)).

The participants are prohibited from using prescription or over-the-counter medications (apart from those described above) within 2 weeks or 5 terminal half-lives, whichever is longer, prior to the first administration of study intervention, during the study, and until the Safety Follow Up Assessment (this includes herbal remedies, vitamins, minerals, antacids and dietary supplements such as fish oils).

6.8.4 Other Interventions

Additional restrictions that study participants should adhere to from Day -1 until Safety Follow Up Assessment are detailed in Section [5.2](#).

7 Discontinuation of Study Intervention and Participant Discontinuation/Withdrawal

7.1 Discontinuation of Study Intervention

A participant must be withdrawn from administration of study intervention if any of the following occur:

- Participant withdraws consent.
- A participant is enrolled but is subsequently discovered not to have met inclusion/exclusion criteria at Screening.
- AEs, if discontinuation of study intervention is considered necessary by the Investigator and/or desired by the participant. This includes in particular AEs of severe intensity and SAEs regardless of its relationship to study intervention.
- Pregnancy

- Protocol noncompliance judged as significant by the Investigator (after discussion with the Sponsor).
- Use of a nonpermitted concomitant drug if clinically relevant as agreed by Sponsor and Investigator, as defined in Section 5.2, where the predefined consequence is withdrawal from study intervention.
- Any events that unacceptably endanger the safety of the participant.

If study intervention is permanently discontinued, the participant will remain in the study to be evaluated for safety. The Schedule of Assessments (Section 1.3) indicates data to be collected at the time of discontinuation of study intervention and follow-up and for any further evaluations that need to be completed.

If a clinically significant finding is identified (including changes from Baseline in QT interval corrected using QTcF) after enrollment, the Investigator or qualified designee will determine if the participant can continue in the study and if any change in participant management is needed. This review of the ECG printed at the time of collection will be documented. Any new clinically relevant finding is reported as an AE.

7.2 Participant Discontinuation/Withdrawal from the Study

- A participant may discontinue from the study at any time, at his/her own request or at the discretion of the Investigator for safety, behavioral, compliance, or administrative reasons.
- The participant may be withdrawn by the Investigator due to participation in another clinical study.
- A participant must be withdrawn if any of the following occurs during the study:
 - Pregnancy.
 - AEs, if study discontinuation is considered necessary by the Investigator and/or desired by the participant. This includes in particular AEs of severe intensity and SAEs regardless of their relationship to study intervention.
 - Use of nonpermitted concomitant medications, as defined in Section 6.8. However, any medications that are considered necessary for the participant's wellbeing (e.g., paracetamol/acetaminophen up to 2 g per day) may be given at the discretion of the Investigator.
 - Protocol noncompliance judged as significant by the Investigator, including noncompliance to the required study considerations (e.g., food/diet requirements), as defined in e.g., Sections 5.1, 5.2, 5.3.1, and 8.
 - Positive for SARS-CoV-2 on admission on Day 11.
- If a participant has failed to attend scheduled study assessments, the Investigator must determine the reasons and the circumstances as completely and accurately as possible.
- If a participant must be withdrawn from the study, the Medical Monitor and clinical study leader for the Sponsor will be informed immediately.
- If there is a medical reason for the withdrawal, appropriate medical care will be provided.

- At the time of study discontinuation, if possible, a discontinuation visit will be conducted, as listed in the Schedule of Assessments (Section 1.3). The Schedule of Assessments specifies the data to collect at study discontinuation and follow-up, and any additional evaluations that need to be completed.
- If the participant revokes consent for the study, any data collected up to that point may still be used, but no future data can be generated, and any biological samples collected will be destroyed.
- A participant has the right at any time to request destruction of any biological samples taken. The Investigator will document this in the site study records and the CRF and inform the Sponsor. The samples will be destroyed.

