9.3 Analyses Sets

The analysis sets are specified below. The final decision to exclude participants from any analysis sets will be made during a data review meeting prior to database lock.

Analysis Set	Description
Screening (SCR)	All participants, who provided informed consent, regardless of the participant's enrollment and study intervention status in the study.
Safety (SAF)	All participants, who were administered any dose of any study intervention. Analyses will consider participants as treated.
Pharmacokinetic (PK)	The PK Analysis Set is a subset of the SAF, and the PK population will include all participants: Who have completed the study without any relevant protocol deviations and factors likely to affect the comparability of PK results. With adequate study intervention compliance. With evaluable PK data, i.e., nonmissing values for primary endpoints. If participants received prohibited concomitant therapy or medicines, as specified in Section 6.8.3, they will be excluded from the PK population. All PK analyses will be based on this analysis set.

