16.1.4 General Specifications for PK Concentration and PK Parameter Data

Predose samples that occur before the first drug administration will be assigned a time of 0 hours, as if the sample had been taken simultaneously with the study intervention administration. Same applies to the pre-dose sample after multiple doses.

Predose or trough samples which have been taken after the subsequent dosing will be reported as a protocol deviation. The resulting concentrations will be included in concentration listings but excluded from descriptive statistics of concentrations and from PK parameter estimation.

Values BLQ will be taken as zero for summary statistics of PK concentration data, PK parameter estimation (e.g. AUC) and for graphical presentations.

Missing concentrations (e.g. no sample, insufficient sample volume for analysis, no result or result not valid) will be reported and used generally as “N.R.”. A participant who withdraws prior to the last planned observation will be included in the analyses up to the time of discontinuation if still included in the PK analysis set.

If samples are collected outside of 10% of the PK sampling time windows defined in the CSP in section 8.4, these will be included in the PK parameter estimation (NCA) but will be excluded from the concentration summary and mean/median concentration plots.

PK concentrations which are erroneous due to a sampling processing or analytical error (as documented in the bioanalytical report) may be excluded from the PK analysis if agreed by the Sponsor. In this case the rationale for exclusion will be provided in the CSR. Any other PK concentrations that appear implausible to the Clinical Pharmacologist/Clinical PK/PD Scientist will not be excluded from the analysis. Any implausible data will be documented in the CSR.

If important protocol deviations occurred likely to affect the PK profile of participants as specified in Section 10.2.1, the impacted concentrations and PK parameters will be excluded from summary statistics and further statistical evaluation.

Any PK concentrations or PK parameters excluded from summary statistics will be included in participants listings and flagged; a reason for exclusion will be detailed in the CSR (e.g. a footnote or a table of exclusions). Any flags should be included in the study specific CDISC data sets.

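### The single completer-only PK Analysis Set drops a valid Day 1/Day 12 Cmax pair when AUC0-infinity is missing or the participant leaves after Day 12

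*Protocol*

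**What the plan says.** **Analysis set.** Protocol 9.3 and SAP 8.1 give the same definition. Members must have completed the study without relevant deviations, complied adequately with dosing, and be evaluable: "With evaluable PK data, i.e., nonmissing values for primary endpoints". The primary endpoints are AUC0-infinity, AUC0-tlast and Cmax (Protocol 3). Both documents base all PK analyses on this one set. Protocol 4.4 counts a participant as a completer only after the Day 20 follow-up. Exclusions are settled at a data review meeting before database lock.

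**Withdrawn participants.** SAP 9.4 assumes missing data are MCAR and includes withdrawn participants up to discontinuation, without qualification. SAP 16.1.4 has them "included in the analyses up to the time of discontinuation if still included in the PK analysis set".

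**Stopping treatment.** Protocol 7.1: "If study intervention is permanently discontinued, the participant will remain in the study to be evaluated for safety". It then adds: "The Schedule of Assessments (Section 1.3) indicates data to be collected at the time of discontinuation of study intervention and follow-up".

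**Revoking consent.** Protocol 7.2 lets results obtained before revocation be used and then limits what follows: "but no future data can be generated, and any biological samples collected will be destroyed". The next bullet is separate: "A participant has the right at any time to request destruction of any biological samples taken".

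**The concern.** Cmax and the AUCs become available at different times. Cmax is fixed once the peak has been sampled. AUC0-infinity depends on the terminal slope, so on the late samples and on what happens during them. A participant-level rule makes Cmax depend on conditions that matter only for AUC, or for neither (the Day 20 visit).

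The completion condition is the more direct route. A participant who leaves on Day 14 is out of the set even if every parameter can be derived.

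Two things are at stake. The first is precision: evaluable pairs are lost for an endpoint that was fully observed. The second is possible selection. Protocol 7.1 and 7.2 name adverse events, in particular severe and serious ones, among the reasons for discontinuation and withdrawal. If people who tolerate the combination badly also have larger Day 12/Day 1 ratios, dropping them pulls the estimate towards no interaction, and the MCAR assumption would be wrong.

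**Working it through.** **1. What is observed, and when (Protocol Table 1).** Post-dose samples after the Day 12 dose:
- Day 12: 1, 1.5, 2, 3, 4, 6, 8, 12 and 16 h = 9 samples.
- Then up to 48 h (Day 14): 24, 30, 38 and 48 h = 4 more, so 13.
- After that: 60, 72, 96, 120, 144 and 168 h = 6. Total 19.

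Provided the peak has passed by the last sample taken, a participant leaving after 48 h has a final Cmax. Under 9.3 that value is not used.

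**2. The rules side by side.** SAP 9.4 includes withdrawn participants up to discontinuation. SAP 8.1 admits only completers to PK analyses. SAP 16.1.4 includes withdrawn participants only if they are still in the set, and the completion condition leaves almost nobody for that clause to cover. SAP 16.1.4 can be read consistently with 8.1; SAP 9.4 cannot, as far as PK analyses are concerned.

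**3. Precision: the plan's own figure first.** The limits in Protocol Table 4 at ratio 1.0 are exp(±h), with

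h = t(0.95, df) × √ln(1+CV²) × √(k/N) × √(χ²(0.80, df)/df).

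With CV = 20%, N = 14, k = 4 and df = N-2 = 12, the t and χ² terms together are 2.0459. So h = 2.0459 × 0.1980 × √(4/14) = 0.2166, giving 0.805 to 1.242 as stated. All 15 upper limits of the ratio-1.0 block reproduce this way.

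Suppose 14 participants have valid Cmax pairs but two are dropped from the set:
- Table 4 formula: 0.805-1.242 becomes 0.786-1.272. The half-width on the log scale grows by ln 1.272 / ln 1.242 = 1.11.
- Paired formula (k = 2, df = N-1), which matches the cross-over: 0.859-1.164 becomes 0.846-1.182, a ratio of ln 1.182 / ln 1.164 = 1.10.

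Either way, the Cmax interval is about 10% wider on the log scale for two avoidable exclusions. The room for loss is 18 - 14 = 4.

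**4. Possible selection (assumption).** The documents give no dropout rate and no link between dropout and exposure. Take 18 assigned and a log-ratio SD of √2 × √ln(1+CV²), which is 0.280 at CV 20%. Simulated factors on the geometric mean ratio:

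| Scenario | 1 lost | 2 lost | 4 lost |
|---|---|---|---|
| CV 20%, highest ratios lost | 0.970 | 0.946 | 0.903 |
| CV 20%, correlation 0.5 | 0.985 | 0.973 | 0.950 |
| CV 20%, correlation 0.3 | 0.991 | 0.984 | 0.970 |
| CV 10%, highest ratios lost | 0.985 | 0.973 | 0.950 |

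**5. Truncated profiles (assumption).** For monoexponential decline with half-life H, the share of the 168 h area reached by time t is (1 - 2^(-t/H)) / (1 - 2^(-168/H)). The documents state no tepotinib half-life. For H = 24 to 48 h, AUC to 72 h is 88% to 71% of the 168 h value, and AUC to 120 h is 98% to 90%. Early departure therefore tends to give a shortened AUC0-tlast rather than a missing one. A shortened Day 12 value set against a full Day 1 value is not a like-for-like ratio.

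**The case against.** The strongest reply is that the plan already has the needed discretion. A data review meeting decides exclusions, SAP 10.2.1 allows individual values to be flagged, and the study is descriptive with no hypothesis test. An AUC obtained after itraconazole was stopped may reflect weaker inhibition, so excluding it for comparability is defensible. A missing AUC should also be uncommon: AUC0-tlast exists for a truncated profile, and SAP 16.1.5.1 keeps a poorly extrapolated AUC0-infinity with a flag.

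These points stand, and they limit how often the rule would bite. They do not answer it for Cmax. Discretion is not a rule, the written definition points to exclusion, and comparability after Day 12 has no bearing on a peak already measured.

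A reader might infer three stronger things that the documents do not support:
- **That a participant who stops treatment is followed for safety alone.** The text says "the participant will remain in the study to be evaluated for safety" but does not exclude other assessments, and it refers to the Schedule. Table 1 ties PK draws to the tepotinib dose. Continued PK sampling is unspecified, not ruled out.
- **That stopping treatment leads to sample destruction.** Destruction follows revoked consent or a request, and results already obtained may be used. No assay timing is given, so loss of a completed Day 1 profile is conjecture. Assaying samples after revocation would contradict the same sentence of 7.2.
- **That the estimate will be biased towards no interaction.** Protocol 2.3.1 describes tepotinib 500 mg as well tolerated, considers the CYP3A4 victim potential low and puts the worst-case P-gp effect at a 43% AUC increase, with the combined effect unknown. No document ties dropout to exposure.

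**Conclusion.** The point holds for the analysis-set definition. Followed as written, Protocol 9.3 and SAP 8.1 discard valid Cmax pairs for reasons unrelated to Cmax, and SAP 9.4 does not fit that rule.

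The size is modest. Two such exclusions from 14 widen the Cmax interval by about 10% on the log scale. Selective loss of one to four participants would multiply the ratio by roughly 0.99 to 0.90 at CV 20%, the lower end only if the four highest ratios were exactly those lost. These factors rest on assumed dropout patterns, so the bias is a plausible risk and not a demonstrated one. The case for acting is that the change is cheap and the margin is four participants.

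**What to change.** 1. **Protocol 9.3 and SAP 8.1.** Apply the non-missing, completion and compliance conditions per parameter and period. For example: for each primary parameter, the analysis includes participants with a valid value on Day 1 and Day 12, with deviations and compliance judged over the time that determines that parameter. A valid Cmax pair then counts whatever the AUC availability or later withdrawal. Say when an AUC0-tlast from a truncated profile is valid.
2. **SAP 9.4 and 16.1.4.** Make both say the same about withdrawn participants, consistent with item 1. List reasons for loss by period so that the MCAR assumption can be judged.
3. **AUC sensitivity.** Report AUC ratios with and without participants who stopped itraconazole before the end of Day 12 PK sampling.
4. **Protocol 7.1 (clarification).** State whether the scheduled PK draws to 168 h continue after itraconazole is stopped, subject to consent.

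Leave the destruction of samples after revoked consent unchanged.

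The cost is wording in the protocol and SAP plus one extra AUC table. The draws are already scheduled. The downside is that N may differ slightly between Cmax and the AUCs, so each table should state its own N.
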